#### 7.1.8 Cue and Traumatic Stress Response Task

The Cue and traumatic stress Response Task will be performed using methodology developed in [name]'s lab, similar to that in used in past studies with alcohol dependent patients and AUD+PTSD/subthreshold PTSD patients [84].. Imagery scripts will be developed at baseline. Traumatic stress imagery scripts will be based on a recent highly stressful situation that the participant identifies as traumatic. Alcohol cue scripts will be developed at baseline. Traumatic stress imagery scripts will be based or a recent event that included alcohol-related stimuli and led to alcohol use. Neutral or relaxing scripts will also be developed. All scripts will be developed by obtaining specific details of stimulus and response, including contextual details, cognitive and verbal content, affective experience, and bodily sensations. These details form the basis of a 5-minute imagery script, which will be developed for each of the three conditions. Imagery sessions will be structured with a 5-minute pre-imagery period, a 5-minute imagery period, and a 5-minute recovery period. Pulse, skin conductance, heart rate variability, and blood pressure

#### #S17-00949

will be monitored during each imagery session with an ADInstruments PowerLab 4/30 Galvanic Skin Response device and a Contec Patient Monitor. In Human laboratory studies with CBD, skin conductance and amygdala activation were reduced by CBD in a closely correlated manner [52], suggesting threat-related sympathetic arousal may serve as a proxy for amygdala activation [53]. Participants will complete Likert scale ratings of vividness, craving, anxiety, and the 30-item Differential Emotion Scale [84] following each of the three periods. After each condition, a progressive relaxation procedure will be implemented to facilitate return to baseline of vital signs, craving and anxiety, an approximate period of 10 minutes, as shown in previous research from the [name] lab [97]. The entire imagery protocol will take 120 minutes. The order of the sessions will be randomized and counterbalanced among participants. The task will be administered at T6, following 4 weeks of treatment with CBD or placebo. At this point, we expect steady- state plasma CBD levels to have been reached.

#### 7.1.9 Alcohol use:

Alcohol consumption will be assessed with a constellation of measures from Time-line Follow-back (TLFB) [78], percent carbohydrate-deficient transferrin (CDT), and breath alcohol concentration (BAC).

# 7.2 Laboratory and Voice-markers Procedures/Evaluations

Plasma will be collected at baseline before treatment, and 45 minutes, 1 day, 1 week, 2 weeks, 4 weeks 6 weeks, and 7 weeks after the first dose of treatment with CBD or placebo. CBD, THC and THC metabolite levels will be obtained from the CBD group only. Anandamide levels will be obtained from both the CBD and placebo groups. Serum will be collected at baseline, at 4 weeks, and at 6 weeks for measurement of CDT.

### 7.2.1 Specimen Preparation, Handling, and Storage

Blood will be drawn at several time points to establish 45 minutes post- and pre-dosing levels of CBD, according to the study's SOP. Briefly, we will measure plasma CBD, THC and THC metabolite levels at baseline, 45 minutes, 1 day, 1 week, 2 weeks, 4 weeks, 6 weeks, and 7 weeks after treatment with CBD. Plasma (1ml/sample) will be stored at -20 °C for no longer than 6 months, and will be labeled with study number, participant number, and timepoint as specified in the MOP. Plasma CBD levels will be determined via High Performance Liquid Chromatography/Tandem Mass Spectrometry (LC-MS/MS) by collaborators at [name] Lab at the Department of Cell Biology at NYU Langone Health.

#### 7.2.2 Specimen Shipment

Specimens will be shipped monthly on dry ice with appropriate labeling for shipment of biological specimens on dry ice, according to the study's MOP. Medical screening labs will be labelled according to CTSI protocols and processed by LabCorp. Plasma for anandamide, CBD, THC and THC metabolite testing will be sent to [name] laboratory at the Department of Cell Biology at NYU Langone Health. A specimen tracking log will be utilized to record dates and times that each specimen was collected and shipped. Specimens may be shipped overnight or walked to [name] lab between 9:00am and 5:00pm on business days.

#### 7.2.3 Voicemarkers Procedure

Voice-markers: Clinical interviews (in-person and remote) will be audio and/or video-taped to ensure quality control and clinical adherence. De-identified audio recordings of participants who consent to participate in the voice-markers analysis will be encrypted and sent via secure sites to HIPAA compliant labs for analysis.

#### 7.2.4 Data Storage and Sharing of Voice-markers Data

Only the investigator and authorized study personnel will have access to the digital audio recordings to ensure quality control, clinical adherence during calibration and to study voice-markers. Under no circumstances will any unauthorized personnel listen to or view the tapes without the written permission of the participant.

The study team will collect speech data from audio recordings collected from the clinical interview at the screening visit. The digital audio recordings will then be transferred for analysis via encrypted CDs or secure NYU sites and stored on secure servers. All the recordings will be de-identified and labeled with a unique study code number for each participant in the study. The study team will identify a professional, specialized entity to conduct the voice-markers analysis; any authorized entity will only receive de-identified data without any PHI or linking information and will store the data on secure servers.

No individual identities will be used in any reports or publications resulting from the study. Study information, such as the digital audio recordings will be coded with a code number unique to the study. Only authorized

#### #S17-00949

NYUMC study personnel, with the permission of the principal investigator, will have access to the files that links the identifying information and study ID codes. Digital audio recordings of interviews will be encrypted and pass-code protected while retained on a secure NYU server until the conclusion of the study; at that point they will be deleted. Only the investigator and study personnel will have access to the digital audio recordings in order to compare the ratings on the standardized interview format. Sessions will be recorded digitally. All files will be secured using a digital encryption key. No unauthorized persons will be able to access this key to open the audio files. These encrypted audio files will be de-identified , stored and password protected on a secure server. Any identifying information embedded in the audio recordings will be deleted during the transcription process. Any data sharing will follow all the NYU data security requirements. Identifiable data will not be stored on laptops, PDA's, flash drives or other portable devices. De-identified data will be shared via mailed encrypted CDs, encrypted emails, or via a VPN access and secure access to the secure NYU server.

# 7.3 Study Schedule

## 7.3.1 Screening Visit (S1) (2 Options)

#### Option 1: Screening Visit – In-Person

- Administer consent quiz (up to 2 administrations) and obtain informed consent of potential participant verified either by signature on written informed consent for screening form or through electronic signature.
- Obtain consent of participant on audio/visual consent form, either by signature on audio/visual consent form or through electronic signature.
- Perform alcohol breathalyzer to obtain BAC
- Review medical and family to determine eligibility based on inclusion/exclusion criteria
- · Perform psychiatric assessments to determine eligibility based on inclusion/exclusion criteria
- Audio-record clinical interview (if participant consents to this component) to ensure clinical quality control, and study voice-markers for participants that consent to voice-marker analysis. Audio recordings can be waived per PI discretion.
- Review concurrent medications to determine eligibility based on inclusion/exclusion criteria
- Perform medical examinations needed to determine eligibility based on inclusion/exclusion criteria
- Obtain demographic information, contact information, alcohol, drug, and tobacco use history and quality of life
- Collect urine for urine drug analysis, urinalysis, urine pregnancy test (if applicable)
- Collect blood at either the One Park site or at CTSI for hepatic function panel/liver function tests (LFT), complete blood count with differential, basic metabolic panel, and serum pregnancy test (if female)
- Record vital signs
- Schedule study visits for participants who are eligible and available for the duration of the study

NOTE: The in-person screening visit may be split into two or more sessions to accommodate participants' schedules, provider availability, etc. All portions of the screening visit must be complete within 1 month.

### Option 2: Screening Visit – Two-part: Clinical Screen Remote; Medical Screen In-Person

To reduce participant burden and minimize in-person screening visits, we will offer participants the option of splitting the screening visit into two or more sessions. The first session will be completed remotely (phone or WebEx) to establish that minimal inclusion criteria and no exclusion criteria are met. Participants will be invited to a second session, which will be completed in-person, if they meet minimum inclusion/exclusion criteria standards. All portions of the screening visit must be complete within 1 month.

Session 1: Clinical Screen – Remote

- Administer consent quiz (up to 2 administrations) and obtain informed consent of potential participant verified either by signature on written informed consent for screening form or through electronic signature
- Obtain consent of participant on audio/visual consent form, verified either by signature on audio/visual consent form or through electronic signature.
- Review medical and family history to determine eligibility based on inclusion/exclusion criteria
- Perform psychiatric assessments to determine eligibility based on inclusion/exclusion criteria
- Review concurrent medications to determine eligibility based on inclusion/exclusion criteria
- Obtain demographic information, contact information, alcohol, drug, and tobacco use history and quality of life

Session 2 – In Person

- Perform alcohol breathalyzer to obtain BAC
- Review medical and family history
- Perform medical examinations needed to determine eligibility based on inclusion/exclusion criteria
- Collect urine for urine drug analysis, urinalysis, urine pregnancy test (if applicable)
- Collect blood at either the One Park site or at CTSI for hepatic function panel/ liver function tests (LFT), complete blood count with differential, basic metabolic panel, and serum pregnancy test (if female)
- Assess withdrawal using CIWA-Ar
- Record vital signs
- Schedule study visits for participants who are eligible and available for the duration of the study.

### 7.3.2 Enrollment/Baseline (B1) (Day 0, 1-30 days after Screening Visit)

- Perform alcohol breathalyzer to obtain BAC
- Record vital signs, results of examination, other assessments, concurrent medications and menstrual calendar (if applicable)
- Record AUD-related and PTSD related measures
- Collect imagery scripts for the cue/traumatic stress response task
- Collect urine for urine drug analysis and urine pregnancy test (if applicable)
- Collect baseline plasma for baseline CBD, THC, and AEA levels (pre-CBD dosing levels)
- Collect blood for carbohydrate deficient transferrin (CDT) test
- Record results of evaluations of safety and psychomotor effects and AUD, PTSD related domains
- Record adverse events as reported by participant or observed by investigator
- Evaluate and record alcohol use
- Administer medical management session
- Provide participants with study medication to administer at visit
- Provide participants with sufficient study medication to administer daily until the next scheduled visit (1 week), and instructions for how to use the study medication and document their use

### 7.3.3 Intermediate Visits

Intermediate visits that do NOT include safety labs may be conducted remotely via phone or WebEx.

### 7.2.2.1 Visit 3

#### 45 minutes +/- 10 minutes (T1)

- Collect blood and plasma for CBD, THC, and AEA levels at 45 minutes post medication (post-CBD levels)
- Record adverse events as reported by participant or observed by investigator
- · Results of evaluations of safety, and psychomotor effects
- Record participant's adherence to treatment program

# 7.2.2.2 Visit 4 (1 day after Baseline/Enrollment Visit +5 days)

#### 1 day (T2)

- Perform alcohol breathalyzer to obtain BAC
- Collect blood and plasma for CBD, Delta-9 THC, 11-Hydroxy Delta-9 THC, Delta-9 Carboxy THC and Anandamide levels (45 minutes post-CBD levels).
- Collect urine for urine drug analysis
- Record adverse events as reported by participant or observed by investigator
- Record vital signs, concurrent medications, and results of evaluations of safety, cognitive function and psychomotor effects
- Record participant's adherence to treatment program
- Evaluate and record alcohol use

## 7.2.2.3 Visit 5

## 1 week (T3)

#### +/- 5 days

- Perform alcohol breathalyzer to obtain BAC
- Collect urine for urine drug analysis and urine pregnancy test (if applicable)
- Collect blood and plasma for CBD, Delta-9 THC, 11-Hydroxy Delta-9 THC, Delta-9 Carboxy THC and Anandamide levels (post- and pre-CBD dosing levels)
- Record adverse events as reported by participant or observed by investigator
- Record vital signs, concurrent medications, menstrual calendar (if applicable), and results of evaluations of safety, psychomotor/subjective effects
- Evaluate and record AUD related measures
- Evaluate and record alcohol use
- Provide participants with sufficient study medication to administer daily until the next scheduled visit (1 week), and instructions for how to use the study medication and document their use
- Record participant's adherence to treatment program
- Administer medical management session

## Version: 4.3 7.3.3.2 Visit 6 2 weeks (T4)

# +/- 5 days

- Perform alcohol breathalyzer to obtain BAC
- Collect urine for urine drug analysis and urine pregnancy test (if applicable)
- Collect blood and plasma for CBD, Delta-9 THC, 11-Hydroxy Delta-9 THC, Delta-9 Carboxy THC and Anandamide levels(post- and pre-CBD levels)
- Collect blood for liver function tests (LFT)
- Record adverse events as reported by participant or observed by investigator
- Record vital signs, concurrent medications, menstrual calendar (if applicable), and results of evaluations of safety, psychomotor/subjective effects
- Evaluate and record alcohol use
- Evaluate PTSD-related measures
- Provide participants with sufficient study medication to administer daily until the next scheduled visit (2 weeks), and instructions for how to use the study medication and document their use
- Record participant's adherence to treatment program
- Administer medical management session

### 7.3.3.3 Phone call 1

# 3 weeks (T5)

#### +/- 5 days

- Record adverse events as reported by participant
- Record participant's adherence to treatment program
- Record concurrent medications, menstrual calendar (if applicable), and results of evaluations of safety

## 7.3.3.4 Visit 7

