The proposed study is a double-blind, randomized proof-of-concept study designed to assess feasibility and contrast effects of CBD treatment to those of placebo on safety, drinking-related outcomes and PTSD/subthreshold PTSD related outcomes in patients with AUD+PTSD/subthreshold PTSD. We will evaluate the safety of an extended daily CBD treatment regimen in an AUD+PTSD/subthreshold PTSD population and measure resulting CBD, THC, and anandamide levels. We will also generate preliminary data on the impact of CBD on alcohol use, PTSD symptoms, a human laboratory traumatic stress induced craving task, neuropsychological and neurophysiological domains implicated in AUD and PTSD/subthreshold PTSD, and cognitive ability. Cannabidiol levels will be obtained from CBD-treated participants to estimate the plasma levels corresponding with putative therapeutic effects and to determine whether dose accumulation occurs. THC levels will be obtained from CBD-treated participants to determine whether CBD metabolites are converted into THC, as has been suggested in the literature [77]. Anandamide levels will be obtained from all participants to test whether CBD elevates plasma anandamide, and to provide preliminary data for relating anandamide levels to putative therapeutic effects. Following screening and baseline assessments, 48 participants will be randomized in a 5:3 ratio to receive either 600mg CBD/day (PO) or placebo respectively for 6 weeks (N=30 participants on CBD and N=18 participants on placebo). Safety measures (adverse events, cognitive and motoric function), drinking related outcomes and PTSD symptoms will be assessed weekly throughout the study. Human laboratory tasks, neuropsychological domains implicated in AUD and PTSD/subthreshold PTSD and cognition will be assessed at baseline and at the end of treatment. Measurement of circulating levels of Delta-9 THC, 11-Hydroxy Delta-9 THC and Delta-9 Carboxy THC will be obtained from CBD-treated participants only at baseline, 45 minutes, 1 day, 1 week, 2 weeks, 4 weeks, 6 weeks, and 7 weeks after treatment with the first dose of CBD vs. placebo. Anandamide levels will be obtained from both CBD- and placebo-treated participants at the aforementioned timepoints.

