# 4 Study Design and Endpoints

# 4.1 Description of Study Design

The proposed study is a phase I/II, single-center, double-blind, randomized proof-of-concept study designed to assess safety and feasibility in the AUD+PTSD/subthreshold PTSD population and contrast effects of CBD treatment to those of placebo on drinking-related outcomes and PTSD symptoms. We will evaluate the safety of an extended daily CBD treatment regimen in an AUD+PTSD/subthreshold PTSD population, measure resulting plasma and CBD and THC levels, generate preliminary data on the impact of CBD on alcohol consumption and PTSD symptoms, assess the effect of CBD on a human laboratory measure of traumatic-stress induced craving and neuropsychological measures relevant to AUD and PTSD/subthreshold PTSD, and assess the effect of CBD dosing no plasma anandamide levels.

150 participants are expected to be enrolled in the study prior to screening and randomization. Following screening and baseline assessments, 48 participants who fully meet study criteria are expected to be randomized in a 5:3 ratio to receive either 600mg CBD/day (PO) or placebo respectively for 6 weeks (N=30 participants on CBD and N=18 participants on placebo). This dose was selected to optimize anxiolytic affects to target stress induced alcohol craving. Assessments of drinking and PTSD related outcomes will be completed at baseline and weekly over 6 weeks of treatment, with an assessment one week following the end of treatment. The human laboratory task and assessments of cognitive function will be completed at baseline and at the end of 6 weeks of treatment. Measurement of circulating levels of CBD, THC, and THC metabolites (Delta-9 THC, 11-Hydroxy Delta-9 THC and Delta-9 Carboxy THC) will be obtained from CBD-treated participants at baseline, 45 minutes, 1 day, 1 week, 2 weeks, 4 weeks, 6 weeks, and 7 weeks after treatment with the first dose of CBD vs. placebo. Anandamide levels will be obtained from both CBD- and placebo-treated participants at the aforementioned time-points.

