# 4.2 Study Endpoints

# 4.2.1 Primary Study Endpoints

The primary study endpoint for alcohol use will be number of drinks per day assessed by the Time Line Follow Back methodology [78]. The primary study endpoint for PTSD symptoms will be the PCL-5 total score. Safety will be assessed by collection of adverse events at all visits after treatment is initiated in addition to LFTs collected at screening, as well as weeks 2, 6, and 7 to assess the liver function during and after treatment

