#### AUD-related measures

The Penn Alcohol Craving Scale (PACS) [79] will be used to assess craving. This scale has 5 Likert-scaled items with excellent internal consistency and evidence of predictive, construct, and discriminant validity. Self-efficacy will be assessed using the Alcohol Abstinence Self-Efficacy Scale (AASE) [81], a self-report questionnaire which has been used widely in the alcohol treatment research, both as a predictor of outcome and as a patient-treatment matching variable [82]. Craving, self-efficacy, and alcohol use will be assessed before treatment (baseline), week 1, week 6, and at one week following the completion of treatment. Mood and Anxiety will be measured with the Beck Anxiety Inventory (BAI) [99] and Beck Depression Inventory-II (BDI-II) [100] scales at baseline, treatment weeks 1, 4 and 6, and at one week following treatment completion.

Risk of suicidality will be assessed by a licensed study provider using the Columbia-Suicide Severity Rating Scale (C-SSRS) [98] as part of each study visit.

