## 5.7.2 Handling of Participant Withdrawals or Termination

Every effort will be made to undertake the protocol-specified safety follow-up procedures to capture AEs, SAEs, and UPs. The investigator will attempt to obtain at a minimum safety/survival data on all participants lost to follow-up. If a participant is lost to follow-up, they study team will attempt to contact the participant up to 15 times by telephone, email, or text message. If the participant fails to respond, locators identified by the participant at screening will be contacted up to three times in the method specified by the participant. If participants withdraw, are terminated, or are lost to follow-up prior to the end of the 6-week treatment phase (prior to T8), they will not be replaced to maintain 48 randomized participants to complete the 6-week treatment phase (through T8) and their partial data will be handled according to the statistical analysis plan (SAP).

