## 7.3.4 Final Telephone Follow-Up

## 9 weeks (T10)

#### +/- 5 days

- Record adverse events as reported by participant
- Evaluate and record alcohol use
- Record evaluations of safety
- Administer treatment completion questionnaires

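### The week-3 and week-5 calls (T5, T7) record no alcohol use although drinking is said to be assessed weekly, so a leaver with no later drinking assessment loses up to 14 days of drinking data (nominal schedule)

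*Combined protocol and SAP*

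**What the plan says.** The protocol describes the timing of drinking assessment in three ways.

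- **Weekly.** Section 2.3 (Rationale) says "drinking related outcomes and PTSD symptoms will be assessed weekly throughout the study". Section 4.1 says "Assessments of drinking and PTSD related outcomes will be completed at baseline and weekly over 6 weeks of treatment".
- **Four occasions.** Section 4.2.2, under AUD-related measures, says "Craving, self-efficacy, and alcohol use will be assessed before treatment (baseline), week 1, week 6, and at one week following the completion of treatment".
- **The visit lists in Section 7.3.** The item "Evaluate and record alcohol use" appears at baseline, T2, T3, T4, T6, T8, T9 and the T10 call. It is absent from Phone call 1 (week 3, T5) and Phone call 2 (week 5, T7). Those two lists hold adverse events, adherence, and "Record concurrent medications, menstrual calendar (if applicable), and results of evaluations of safety".

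Section 7.1.9 names the alcohol measures but sets no schedule, so it does not settle the matter.

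The endpoint is defined in Section 4.2.1: "The primary study endpoint for alcohol use will be number of drinks per day assessed by the Time Line Follow Back methodology". For people lost to follow-up, Section 5.7.2 says "The investigator will attempt to obtain at a minimum safety/survival data on all participants lost to follow-up". It leaves the treatment of partial data to the SAP. No TLFB at withdrawal is described.

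**The concern.** Drinks per day is a primary endpoint, and from week 2 to week 6 every second scheduled contact does not collect it. Someone who takes the week-3 call and then disappears contributes no drinking data after T4, although staff had them on the telephone.

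The days concerned feed several planned analyses:

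- the MMRM on the ITT set and the estimates averaged over the treatment period (Sections 20.3.1 and 20.3.2);
- the weekly drinking endpoints, such as heavy, very heavy and abstinent days (Section 4.2.2);
- the first week of a sustained 50% fall in drinking (Section 20.3.10).

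An MMRM handles missing visits by relying on what was observed before them. If some people leave because their drinking has changed, the unrecorded stretch is where that change would show.

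**Working it through.** The plan gives no figure for this loss, so there is none to reproduce.

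**1. Could the safety item cover drinking?** No. The T10 call lists alcohol use and safety evaluations as separate items. T10 also shows that the protocol accepts collecting drinking by telephone.

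**2. Gap between drinking records.** Nominal days are T4 = 14, T5 = 21, T6 = 28, T7 = 35, T8 = 42, each ±5 days.

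| | Nominal longest gap | Longest gap with windows |
|---|---|---|
| As written (T4–T6, T6–T8) | 28 − 14 = 14 | (28 + 5) − (14 − 5) = 24 |
| With T5 and T7 recording | 21 − 14 = 7 | (21 + 5) − (14 − 5) = 17 |

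The T6–T8 interval gives the same values.

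**3. What later recall can recover.** No TLFB look-back is stated for treatment visits. The only one given is 30 days, at the clinical re-screen (Section 7.3.6). Assume that 30 days applied throughout:

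- At T6 or T8 it would cover even the 24-day gap.
- At T9 (day 49) it would reach back to day 19. That covers someone last recorded at T6 (49 − 28 = 21 days) but not fully someone last recorded at T4 (49 − 14 = 35 days).
- At T10 (day 63) it would reach back to day 33, short of both T6 (63 − 28 = 35 days) and T4 (63 − 14 = 49 days).

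Recovery is therefore complete for attenders and partial for people found late.

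**4. Mean loss per leaver.** Assume leaving times are uniform over days 14 to 42 and there is no later drinking assessment.

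- As written: time since the last record is uniform on 0 to 14, mean 14 / 2 = 7.0 days.
- With T5 and T7 recording and every call completed: uniform on 0 to 7, mean 7 / 2 = 3.5 days.

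**5. Total loss.** No dropout rate is given. The follow-up rate of 90% in Section 5.4 is a trigger for reviewing tracking, not an assumption about dropout. Take 10% to 30% of 48 leaving uniformly over 42 days.

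- Leavers: 4.8 to 14.4.
- Leaving in days 14 to 42: × 28/42 = 3.2 to 9.6.
- Person-days lost as written: × 7.0 = 22.4 to 67.2.
- Person-days lost with the calls recording: × 3.5 = 11.2 to 33.6.
- Planned person-days: 48 × 42 = 2016. The loss is 1.1% to 3.3% as written and 0.6% to 1.7% with the change.

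**The case against.** The strongest defence is that TLFB is a retrospective daily record. T6 and T8 can each cover the preceding two weeks, so weekly values remain derivable for everyone who attends. That stands, provided the look-back is long enough.

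Section 5.7.2 also sets safety and survival data as a minimum, with up to 15 contact attempts plus locators. Section 20.3.5 separates stopping the intervention from stopping follow-up, and T9 and T10 record alcohol use. So not everyone who stops treatment loses data; the loss falls on leavers with no later drinking assessment. This also stands.

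A leaver has no week-6 value with or without the calls, and the primary contrast is at week 6. Section 6.1.9 restricts the primary analyses to those who complete treatment through T8, and under that rule these days do not enter the primary analysis at all. They do under the ITT set of Section 20.3.1, which needs only one dose and one post-baseline efficacy measurement. The two sections conflict, so the objection is only as strong as Section 6.1.9.

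A reader might infer that two-thirds of the drinking data are at risk, because 28 of the 42 treatment days lie in the two 14-day intervals. That is the share of days in those intervals, not the share lost. A reader might also infer that the MMRM result is biased by dropout after relapse. The documents offer no evidence that dropout follows relapse or differs by arm, so this remains a possibility.

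**Conclusion.** The omission and the conflict with weekly assessment are plain in the text. The consequence is real but small: up to 14 days per affected leaver nominally (24 at the window extremes), and about 22 to 67 person-days in all, or 1% to 3% of the planned total. The totals rest on assumed dropout of 10% to 30%, uniform leaving times and no later drinking assessment.

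The loss touches the ITT MMRM, the treatment-period averages, the weekly drinking endpoints and the week of onset. It does not touch a primary analysis restricted to completers. Nothing here shows that the treatment comparison is biased. The case for change is that the data are cheap to collect on calls already scheduled and may not be recoverable once a participant is gone.

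**What to change.** - Add "Evaluate and record alcohol use" to the T5 and T7 call lists, as at T10, with TLFB going back to the last recorded day. State that look-back rule for all treatment and follow-up contacts.
- Attempt the same TLFB at withdrawal or termination. The calls help only leavers who answer them.
- Make Sections 2.3, 4.1 and 4.2.2 agree with the visit lists on when drinking is assessed.
- In Sections 2.3 and 4.1, correct the weekly wording for PTSD symptoms to baseline and weeks 2, 4, 6 and 7, as Sections 4.2.2 and 7.1.7 give for the PCL-5.
- Reconcile Sections 6.1.9 and 20.3.1 on who enters the primary analysis.

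The cost is a few minutes on each of two calls, an added case report form entry for each, and slightly more participant burden. The rest is wording.
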